6. SAMPLE AND RECRUITMENT

6.1. ELIGIBILITY CRITERIA

Inclusion criteria

Children (aged 5-15 years inclusive) will be suitable for inclusion in the study if they have:

- A proven low-risk ankle fracture on x-ray
 - o minimally displaced or undisplaced fibular fracture
- A clinical undisplaced fracture which fulfils the Ottawa criteria:
 - o A history of trauma
 - o Tenderness at the posterior edge of the lateral malleolus
 - Unable to weight bear for more than 4 steps
 - o No alternative cause of pain identified on x-ray

Exclusion criteria

Children will be excluded if

- The injury is more than 7 days old at randomisation
- They in conjunction with their parents are unable to complete the outcome measures chosen in English.

• The child is on the Child Protection Register or where there is any concern about the cause of the injury.

Expected duration of participant participation

Study participants will be participating in the study for 12 weeks

Removal of participants from therapy or assessments/Participant Withdrawal

Participants may be withdrawn from the trial either at their own request or at the discretion of the Investigator. The participants will be made aware that this will not affect their future care. Participants will be made aware (via the information sheet and consent form) that should they withdraw the data collected to date cannot be erased and may still be used in the final analysis. Enrolled participants in the ANCHOR TRIAL who are not yet randomised can be replaced (though keeping their trial ID), but participants who withdraw after randomisation will not be replaced.

6.2. SIZE OF SAMPLE

No formal sample size calculation is required for the feasibility trial. An estimate for the sample size of the full trial requires 969 patients for 90% power with a MCID for ASK-P of 5 and standard deviation of 16.5⁹. Assuming a 30% loss to follow up, for feasibility this requires 42 patients to be recruited into each group of the feasibility study.

6.3. RECRUITMENT

Participants will be recruited from the Emergency Department, acute fracture or injury clinics. The initial approach will be from a member of the patient's usual care team (which may include the investigator), and information about the trial will be on display in the relevant clinical areas in the form of posters and information leaflets. Only members of the patient's existing clinical care team will have access to patient records without explicit consent in order to identify potential participants, check whether they meet the inclusion criteria or make the initial approach to patients.

The investigator or their nominee, e.g. from the research team or a member of the participant's usual care team, will inform the participant or their nominated representative (other individual or other body with appropriate jurisdiction), of all aspects pertaining to participation in the study.

If needed, the usual hospital interpreter and translator services will be available to assist with discussion of the trial, the participant information sheets, and consent forms, but the consent forms and information sheets will not be available printed in other languages.

It will be explained to the potential participant that entry into the trial is entirely voluntary and that their treatment and care will not be affected by their decision. It will also be explained that they can withdraw at any time, but attempts will be made to avoid this occurrence. In the event of their withdrawal it will be explained that their data collected so far cannot be erased and we will seek consent to use the data in the final analyses where appropriate.

Participants who are eligible for the study and are approached by the research team but decline to participate will be invited to provide their contact details so they may be invited to join an interview with the research team at the end of their child's treatment.

6.4. CONSENT

Written informed consent will be obtained before any participant enters the main study. All participants will require a written consent form completed by a person with parental responsibility. If a child wishes to assent, this may be documented on the consent form. Where a child and the person with parental responsibility disagree, then the child will not be recruited. Separate consent forms will be used for children entering the ANCHOR Trial and those participating in interviews. Participants consenting for the ANCHOR Trial will be asked to provide additional, optional consent to be contacted for a qualitative interview. A written information sheet about the interview will be provided to parent/child dyads who decline the main study but consent to interview. The researcher will go through the information sheet and answer any questions prior to the provision of a written informed consent form for trial participants, or verbal informed consent in the case of non-trial participants who have declined the main study. The consent forms for the interview study are separate to the main consent form for the trial to allow participants to consent to either half of the study dependent on their individual preferences. Individuals taking part in the RCT do not have to participate in the interview study, and individuals who decline participation in the RCT should be offered the opportunity to participate in the interview study.

The Informed Consent Form will be signed and dated by the participant's parent or legal guardian before they enter the study. The Investigator will explain the details of the trial and provide a Participant Information Sheet, ensuring that the participant has sufficient time to consider participating or not. The Investigator will answer any questions that the participant has concerning study participation.

As all participants will be children under the age of 16, the Participant Information Sheets include a child-friendly study summary that has been piloted with children aged 5-15. No child will enter the study without parental or legal guardian consent and, where appropriate, will give assent that will be documented on the same consent form. Where Consent is given, and assent is refused the child will not be recruited to the study.

Informed consent will be collected from each participant before they undergo any interventions (including physical examination and history taking) related to the study. One copy of this will be kept by the participant, one will be kept by the Investigator, and a third will be retained in the patient's hospital records.

Should there be any subsequent amendment to the final protocol, which might affect a participant's participation in the trial, continuing consent will be obtained using an amended Consent form which will be signed by the participant.

6.5. DURATION OF PARTICIPANT INVOLVEMENT

The study duration from first recruitment to final follow up: 18 months (1/10/2020 - 1/4/2022). Participants in the trial will be involved in the study for 12 weeks. Patients contributing to the interviews will be involved for a total of 24 weeks. The end of the study will be the last postal return (12-week follow up) of the last participant.

7. ETHICAL AND REGULATORY CONSIDERATIONS

7.1. ASSESSMENT AND MANAGEMENT OF RISK

Trial participants

Trial participants will be monitored for adverse events as detailed below. Where researchers become aware of any suspected or alleged abuse of children or vulnerable adults in the course of this research then the local NHS safeguarding policy will be followed. Specifically, if a researcher:

- a) suspects that a child or adult at risk has been, or is at risk of being abused;
- b) has had a disclosure of abuse made to them;
- c) receives a complaint relating to young person or adult at risk safeguarding issues at the hospital;
- d) is contacted by a local authority as part of its enquires about a child that might be suffering or at risk of suffering significant harm

Then the researcher will report the matter with the Chief Investigator who will seek advice from the Lead Safeguarding Officer for the NHS site. This will be escalated and documented in line with the local policy.

Interviews

It is not anticipated that the conduct of interviews with parents/carers and children within this study will generate major ethical issues. The content of the interviews is unlikely to uncover particularly sensitive issues to the child or their family, but where participants are becoming upset or distressed the interviewer will be empowered to amend the questions recommended in the interview schedule or postpone or terminate the interview if required.

Researchers will be subject to the local fieldwork policy where researchers are conducting interviews at the participant's homes or outside of the hospital or university premises. This requires a risk assessment to be completed and authorised by the relevant safety officer prior to any fieldwork being initiated.

7.2. RESEARCH ETHICS COMMITTEE (REC) REVIEW & REPORTS

Before the start of the study, approval will be sought from a REC for the study protocol, informed consent forms and other relevant documents e.g. advertisements.

Substantial amendments that require review by REC will not be implemented until all the appropriate regulatory bodies grant a favourable opinion for the study (note that amendments may also need to be reviewed and accepted by R&D departments, or through other research governance mechanisms, before they can be implemented in practice at sites).

All correspondence with the REC will be retained.

It is the Chief Investigator's responsibility to produce the annual reports as required. The Chief Investigator will notify the REC of the end of the study.

CONFIDENTIAL ANCHOR Trial Protocol v3.2 28.02.22 IRAS ID 277534 page 24 of 33
FUNDED BY
NIHR National Institute
for Health Research

An annual progress report (APR) will be submitted to the REC within 30 days of the anniversary date on which the favourable opinion was given, and annually until the study is declared ended. If the study is ended prematurely, the Chief Investigator will notify the REC, including the reasons for the premature termination. Within one year after the end of the study, the Chief Investigator will submit a final report with the results, including any publications/abstracts, to the REC.

7.3. PEER REVIEW

The study protocol was peer-reviewed as part of the NIHR RfPB funding award.

7.4. PATIENT & PUBLIC INVOLVEMENT

This research plan will maintain the parent and public involvement throughout the study period. A sequence of face-to-face parent involvement focus groups will be used to develop the study design, delivery and dissemination. These will be supplemented with the use of virtual parent and patient involvement activities with parental representation on the study management panel.

Following feedback regarding hosting parent involvement groups at the Nottingham University Hospital Site where parking is difficult, and childcare is limited we have decided to host parent and patient involvement groups at suitable family friendly venues such as Twycross Zoo. Four focus group sessions are planned over the two-year study period to coincide with school holidays. The programme for the focus groups is flexible to accommodate for any unseen issues with the study delivery. It is anticipated to include: screening of the description of outcomes for inclusion in the Delphi survey, face validity and acceptability of secondary outcomes for inclusion in the trial, retention strategies for the trial and dissemination of findings.

In order to maintain collaboration with our international PPI panel, further electronic communication will be sent to the virtual PPI group. This group will be sent out regular newsletters documenting study progress and will be consulted using electronic survey for wording of questions for the Delphi survey. The virtual PPI group will be an important avenue for dissemination of study findings.

The study has a parent co-applicant who has experience in managing children with injuries both as a mother and as a schoolteacher. She will be an important member of the study management panel ensuring study acceptability, deliverability and in the dissemination of research findings. PPI training will be provided from the University of Nottingham.

Expenses for all PPI participants is being provided in line with INVOLVE guidelines

7.5. REGULATORY COMPLIANCE

Before any site can enrol patients into the study, the Chief Investigator will apply for and receive HRA approval for the study

Prior to commencing recruitment, sites must confirm their capacity and capability to conduct the study, as per the HRA approval letter.

Any amendment to the protocol should be considered that it may potentially affect a site's capacity to continue in the study, the Chief Investigator/ Principal Investigator or designee will inform the Sponsor of the proposed amendment. The amendment will be submitted as per Section 8.7.

7.6. PROTOCOL COMPLIANCE

Accidental protocol deviations can happen at any time. They must be adequately documented on the relevant forms and reported to the Chief Investigator and Sponsor immediately.

Deviations from the protocol which are found to frequently recur are not acceptable, will require immediate action and could potentially be classified as a serious breach.

7.7. AMENDMENTS

It is the sponsor's responsibility to decide whether an amendment is substantial or non-substantial for the purposes of submission to the REC. If the sponsor wishes to make a substantial amendment to the REC application or the supporting documents, the sponsor must submit a valid notice of amendment to the REC for consideration. The REC will provide a response regarding the amendment within 35 days of receipt of the notice, informing the HRA of the amendment. Site R&D departments will also need to be provided with the information on the amendment. Their level of review will be dictated by the category as assessed by the REC or HRA (A, B or C).

Non-substantial amendments also need to be notified to the HRA as well as the relevant R&D departments of participating sites to assess whether the amendment affects the continued capacity for that site. Note that some amendments that may be considered to be non-substantial for the purposes of REC and/or MHRA, may still need to be notified to REC and/or MHRA (e.g. a change to the funding arrangements).

7.8. Adverse Event

Potential adverse events

Table 4 lists adverse events reported in previous trials of childhood low-risk ankle fractures.

Children participating in the ANCHOR Trial will be screened at clinical follow up for the following potential adverse events:

- Pressure related issues
 - o Heel pain
 - o Blisters
 - o Sores
- Skin irritation or rashes
- Persistent swelling
- Persistent bruising
- Additional visits to healthcare providers (e.g. physiotherapy, fracture clinic etc)

Table 4 Adverse events reported in previous trials of "low-risk" ankle fractures

Trial	Adverse events	
Boutis et al 2007[18]¤	Unscheduled visits to healthcare provider	
	Skin irritation / rash	
Barnett et al 2012[19]	Additional visits to healthcare provider	
	Pressure related complications	
Gleeson et al 1996[16]	No adverse events reported	
Launay et al 2008[17]	Persistent swelling and bruising	

Reporting Procedures

Proportionate to the type of study and participant involvement, all adverse events should be reported. Depending on the nature of the event the reporting procedures below should be followed. Any questions concerning adverse event reporting should be directed to the Chief Investigator in the first instance.

Non serious AEs

All such events, whether expected or not, should be recorded.

Serious AEs

An SAE form should be completed and sent to the Chief Investigator within 24 hours. Hospitalisations for elective treatment of a pre-existing condition do not need reporting as SAEs.

All SAEs should be reported to the Derby REC where in the opinion of the Chief Investigator, the event was:

'related', ie resulted from the administration of any of the research procedures; and

'unexpected', ie an event that is not listed in the protocol as an expected occurrence

Reports of related and unexpected SAEs should be submitted within 15 days of the Chief Investigator becoming aware of the event, using the NUH SAE form for non-CTIMP studies.

Local investigators should report any SAEs as required by their Local Research Ethics Committee and/or Research & Development Office.

The Sponsor Contact Details for SAEs are:

- Email ([contact])
- Hand delivered not mailed ([name])
- [contact]) if written report not immediately possible

Any queries please contact a member of staff in the Nottingham University Hospitals Research & Innovations department:

- [contact]
- Email: [contact]

Participant removal from the study due to adverse events

Any participant who experiences an adverse event may be withdrawn from the study at the discretion of the Investigator.

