3.4. PROGRESSION CRITERIA

The trial will progress to a full trial if all the following are fulfilled:

- 1. A suitable outcome measure can be determined using the feasibility data and the effect size of the three interventions estimated along with the standard deviations in order to properly power a definitive trial;
- 2. None of the interventions have an unacceptable complication rate as agreed by the trial steering committee;
- 3. Recruitment rates are greater than 50% anticipated allowing a full trial to be completed within a 3-year time frame within the U.K. Trauma Trials Network;
- 4. Study retention is greater than 60% at the 6-week follow up in all groups;
- 5. The effect size and standard deviation produces a sample size calculation that can be achieved across the trauma trials network within a reasonable time frame and within scope of an NIHR HTA funding;

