4.2. DETAILS OF PRODUCT(S)

The ANCHOR Trial is a randomised, feasibility trial. This design will permit evaluation of trial feasibility and deliver validation data for outcome instruments used in childhood lower limb fractures.

Products will be prescribed for the ANCHOR Trial population. Participants will be randomised to receive a supportive bandage, removable brace or walking cast.

Product Description

- 1. Supportive bandage. An elastic bandage (e.g. tubigrip) will be provided for the child to wear for two weeks. The bandage will be sized according to manufacturer instructions.
- 2. Semi-rigid, removable brace (including splints or custom orthoses). A removable ankle brace (e.g. Aircast Air-Stirrup Ankle Brace, removable weightbearing backslab Walker boot or Aircast boot) will be prescribed at the discretion of the local treating physician. The device will be sized and fitted according to manufacturer instructions.
- 3. Below knee walking cast. A non-removable, below knee walking cast will be applied according to local protocols. The cast may be synthetic or resin based and will be applied over standard padding. The cast will be circumferential or a backslab but must be constructed to bear weight and will be applied and removed by a trained member of staff.

Manufacture

Local NHS supply chain approved devices will be prescribed in each centre and used according to manufacturer guidelines.

Known Side Effects

Previously reported side effects of treatments include:

Pressure related injuries e.g. marks and blisters – This is more common in the removable brace group than cast group and is associated with patients not wearing the supplied protective sock [22]. This will be mitigated by reminding this group to wear the sock and by ensuring patients in brace or cast have adequate padding.

Plaster saw injuries – removal of a below knee walking cast requires the use of an electronic oscillating plaster saw which may cause injury. Injury is typically caused through thermal damage to the skin. This will be reduced by requiring casts to be applied and removed by trained and experienced personnel. This is in line with the 2015 British Orthopaedic Association Casting Standards (https://www.boa.ac.uk/uploads/assets/uploaded/83dcfe25-307e-4e82-abf362976f08a3ae.pdf)

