5.1. STUDY ACTIVITIES FOR THE TRIAL

At time of diagnosis (typically in the Emergency Department), potential participants may be identified and provided with a patient information sheet by the usual care team. Screening of participants may also be performed by the usual care team in face-to-face or virtual fracture clinics and information sheets provided.

CONFIDENTIAL ANCHOR Trial Protocol v3.2 28.02.22 IRAS ID 277534 page 19 of 33
FUNDED BY
NIHR National Institute
for Health Research

Where eligible participants wish to join the study, a member of the research team will obtain informed consent and undertake randomisation to a product at the point in the local care pathway where a definitive treatment is being offered. This may be in the Emergency Department, Emergency clinics or fracture clinic depending on the local pathways.

Following completion of pre-injury baseline scores and CRF, the patient will be randomised using a web-based electronic randomisation with 1:1:1 allocation with stratification for fracture type (occult and visible fracture line) and child age (5-10, 11-15) with block sizes of 3, 6 & 9.

Treatment will be provided according to random allocation by a trained member of the clinic staff according to the manufacturer's guidelines. As described in section 4.2, the available treatments are:

- 1. Supportive bandage.
- 2. Semi-rigid, removable brace (including splints or custom orthoses).
- 3. Below knee walking cast

Routine follow up will be provided according to local protocols and decided by the usual care team. Patients who have a below knee walking cast are likely to require a clinic review to remove the device. Other patients may be discharged with instructions to remove their own device at home.

A patient diary is provided to participants at time treatment is provided. The diary is returned after two weeks.

Outcome assessment will be completed by the central research team using an electronic interface through the Redcap system. Outcomes will be collected at 2 weeks, 6 weeks and 12 weeks. Telephone, SMS text messages (Esendex, Nottingham) and e-mail reminders will be used to encourage completion of outcome scores.

	Baseline (pre- injury) score	Review 1 (Day 7-23)	Review 2 (Day 35-52)	Review 3 (Day 84-100)
Demographics	Х			
Physical function (PROMIS Mobility)	х	х	Х	Х
Quality of life (EQ-5D-Y)	х	Х	х	Х
Daily pain (faces pain or VAS)	х	Х		
Re-injuries			Х	Х
Complications		Х	Х	Х
Parent satisfaction			Х	Х
Child satisfaction			Х	Х

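### The adverse-event list in section 7.8 does not prompt for plaster saw injury, the cast-only harm named in section 4.2, so cast-arm complications may be under-ascertained

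*Protocol*

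**What the plan says.** Section 4.2, Known Side Effects, describes two harms. Pressure-related injury is reported as more common with the removable brace than with the cast. The other is saw injury: "removal of a below knee walking cast requires the use of an electronic oscillating plaster saw which may cause injury". Only the cast arm is exposed to it.

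Section 7.8 sets out what is asked about: "Children participating in the ANCHOR Trial will be screened at clinical follow up for the following potential adverse events". The items are pressure issues (heel pain, blisters, sores), skin irritation or rashes, persistent swelling, persistent bruising, and "Additional visits to healthcare providers (e.g. physiotherapy, fracture clinic etc". Saw injury is not among them. For non-serious events the same section adds: "All such events, whether expected or not, should be recorded".

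Table 3 in section 5.1 marks Complications at Reviews 1, 2 and 3, with outcomes collected centrally through an electronic interface.

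Complications are used twice. Objective 1b asks whether the treatments have any. Progression criterion 2 in section 3.4 requires: "None of the interventions have an unacceptable complication rate as agreed by the trial steering committee". All the criteria must be met for progression.

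**The concern.** The protocol recognises two device harms and solicits only one. The one it asks about by name is weighted towards the brace; the one it does not ask about can occur only with the cast. Events that are asked about by name tend to be reported more completely than events that must be volunteered. The completeness of the complication record may therefore differ by type of harm, and one type belongs to a single arm.

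The steering committee could then see a cast-arm complication profile that lacks a harm the protocol itself anticipated. This is a question of what is asked at collection. An analysis plan cannot recover an event that was never elicited.

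**Working it through.** The protocol states no complication or saw-injury rate, so there is no figure to reproduce. The main check sets the lists side by side.

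| Harm | Named in 4.2 | In Table 4 (previous trials) | Prompted in 7.8 |
|---|---|---|---|
| Pressure injury | Yes, more common with brace | Yes | Yes, three sub-items |
| Plaster saw injury | Yes, cast only | No | **No** |
| Skin irritation or rash | No | Yes | Yes |
| Persistent swelling, bruising | No | Yes | Yes |
| Additional or unscheduled visits | No | Yes | Yes |

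Every event in Table 4 appears in the prompted list. The only known side effect in 4.2 that is missing from the list is also missing from Table 4. The list looks as if it was drawn from the earlier trials and not checked against 4.2; that is an inference.

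**Would the event reach the trial record unprompted?** Three statements bear on this.

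1. Section 4.3 has devices removed by nursing staff independent of the trial, for children who need an appointment for cast removal, and has follow-up done remotely by the central team. The person who sees the injury is not the person who collects the outcomes.
2. Appendix 2 places device removal at 2 weeks (day 14). Table 3 allows Review 1 from day 7 to day 23. A Review 1 completed on days 7 to 13 would precede removal on day 14.
3. The next collection would then be Review 2, on days 35 to 52. That is 35 − 14 = 21 to 52 − 14 = 38 days after removal, and would rely on unprompted recall.

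**Illustration of size, on assumed rates.** Let n = 42 cast participants (section 6.2), all having saw removal. Let s be the saw-injury rate and c the share recorded without a prompt. The protocol gives neither s nor c.

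- Expected injuries = n × s
- Chance of at least one = 1 − (1 − s)^n
- Expected injuries not recorded = n × s × (1 − c)

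| s | Expected of 42 | Chance of at least one | Missed if c = 0 | Missed if c = 0.5 | Missed if c = 1 |
|---|---|---|---|---|---|
| 1% | 0.42 | 1 − 0.99^42 = 34% | 0.42 | 0.21 | 0 |
| 2% | 0.84 | 1 − 0.98^42 = 57% | 0.84 | 0.42 | 0 |
| 5% | 2.10 | 1 − 0.95^42 = 88% | 2.10 | 1.05 | 0 |

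The cast-arm rate is understated by at most s × (1 − c), provided the child has no other recorded complication. Over this range that is 0 to 5 percentage points. One child in 42 is 1/42 = 2.4 points.

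**The case against.** The strongest reply is that nothing is lost. Section 7.8 requires all adverse events to be reported, Table 3 collects complications three times in every arm, and 4.2 requires trained staff to remove casts, so an injury would happen in front of someone. A saw burn might also be entered under skin irritation. The steering committee reviews all adverse events. The event form is not shown and may already name the harm.

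Much of this stands: a saw injury is recordable, and the loss could be nil. What it does not establish is equal ascertainment. One harm is asked about and the other must be offered. The staff present at removal are independent of the trial, and a burn entered as skin irritation could not be identified as a saw injury.

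Two stronger readings are tempting, and the protocol does not support them.

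- A reader might infer that complication rates cannot be compared across arms, so that criterion 2 fails. Criterion 2 is a judgement on each intervention by the steering committee, with no numerical threshold and no between-arm test. The net direction between arms is also unknown. Screening takes place at clinical follow-up, which cast children are likely to attend, while "Other patients may be discharged with instructions to remove their own device at home". That could make detection of the prompted items more complete with the cast.
- A reader might infer that the visits item turns each cast-removal appointment into an adverse event. Section 5.1 does say: "Patients who have a below knee walking cast are likely to require a clinic review to remove the device". But this follows directly on "Routine follow up will be provided according to local protocols and decided by the usual care team", and Appendix 2 schedules device removal. The item covers only additional visits, which most naturally means visits beyond those planned. The word is undefined, but no rule counts removal visits, and any figure built on counting them would rest on a reading that the surrounding text opposes.

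**Conclusion.** The point holds in a limited form. Section 7.8 does not prompt for a harm that 4.2 names and that only one arm can suffer, so that harm may be under-ascertained relative to the harms asked about by name. This affects the completeness of the evidence for objective 1b and criterion 2. It does not show that either is invalid or that the arms cannot be compared.

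The likely size is small: 0.4 to 2.1 expected events in the cast arm if the true rate is 1% to 5%, of which anything from none to all might go unrecorded. Both ranges are assumptions. The conclusion also assumes that the event form follows the 7.8 list. If the form already names saw injury, only the protocol text needs correcting.

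The missing definition of an additional visit is a minor wording matter. This is a cheap improvement to data collection.

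**What to change.** Add plaster saw injury, described as a skin burn or cut at cast removal, to the prompted list in section 7.8 and to the Complications item in Table 3 at Reviews 1, 2 and 3. Asking at all three reviews covers children whose Review 1 falls before the cast comes off.

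As a clarification only, add to 7.8 that planned device removal and reviews that are routine at the site do not count as additional visits.

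The cost is one extra item on the electronic review form and a line or two in 7.8. Treatment, visit schedule and sample size are unchanged.
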